5.1. Mortality Study

5.1.1. Core Elements (Malawi, Niger, and Tanzania)

In all three study sites, we will conduct the following study activities for the mortality study:

Training

Before the baseline visit, the University of California San Francisco (UCSF) team will certify local team members at all three study sites. Standardization activities before each biannual census will consist of didactic classroom instruction and mock census activities, followed by in-field training to harmonize protocols.

Census

An enumerated population census for 0 - 60 month olds (focusing on this age group) will be conducted every 6 months by trained field workers masked to study arm, recording births, deaths, and migration of children eligible for treatment. Pregnant women will be noted at each census, to maximize inclusion of newborns on the subsequent census.

Random Census Verification

A repeat census will be conducted in a random selection of households at each study visit. Personnel will be different from the original census. This will allow us to assess whether the census team identified all births, deaths, and migratory episodes relative to the previous census.

Verbal Autopsy

Each of the study sites will perform a verbal autopsy for all children (aged 1-60 months) identified as having died during the study.³⁹

Treatment

Children aged 1-60 months on the current census will be offered weight- or height-based (<1 year weight and children who cannot stand; ≥1 year height), directly observed, oral azithromycin suspension (or oral placebo) every 6 months for 2 years as performed in trachoma programs in each of the 3 countries. Specifically, individuals are eligible on or after their one month birthday, and prior to the day of their fifth birthday.

Antibiotic Coverage Surveillance

We will estimate antibiotic coverage from the most recent biannual census records. At the end of each treatment round at months 6, 12, and 18, we will identify any children who have missed 2 or more consecutive treatments, and forward this information to the census team.

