The site study coordinator will supervise all census activities. Formal checks of census quality will be conducted through the random census verification. In addition, the study coordinator will visualize all censused households using imagery from GoogleMaps. The goal of this activity will be to minimize the chances of missing large neighborhoods or specific regions within study communities. The study coordinator will also check the data entry progress for each community, paying special attention at the follow-up censuses, as to whether there are any missing data for the “vital status” variable (i.e., present, dead, absent). Once the study coordinator is confident that the entire community has been reached, and that the amount of missing data are acceptable (defined as <10% of children in a community), the study coordinator (or other research team member) will certify the census data collection for that community complete via Salesforce. Changes can be made to the record at different time points, but these changes will not be reflected until the subsequent census. All changes are time and date stamped in the database.

Census Timing

The census will be performed prior to each mass azithromycin/placebo distribution. Study sites may choose to perform the census activities over a discrete time period (e.g., all communities completed over a 1-month period, requiring census activities to take place simultaneously in many communities at once) or alternatively in a “rolling” fashion (e.g., all communities completed over a 6-month period, requiring fewer census teams to be active at once). In either case, each community must be censused every 6 months, so it may not take more than 6 months to complete all communities. The census must be completed (i.e., “locked”) at the household level before treatment can be given.

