## 3 Analysis

The primary outcome is mortality, analyzed in the same way as in MORDOR Stage I, i.e., present on an initial census, and absent on the next follow-up census due to death. Since the study has been extended, the same analytic template will be used for each visit, e.g. at 48, 54, and 60 months. Each visit that is conducted will be reported.

Study A:

1. Sample size considerations.
  - a. Assuming communities of size 668 with approximately 17% in the target age range, an effect size of 20%, 10% loss to follow-up per year, 2% mortality per year, and a CV of 0.51, 312 communities per arm provides approximately 87% power (see MORDOR Phase I SAP for details).
  - b. Updating based on data from Phase I (Niger), we find the following. Assuming the observed CV of 0.34, a death rate of 2% per year results in approximately 80% power to detect a 17% effect. A death rate of 2.5% per year (and a CV of 0.34) result in approximately 80% power to detect a 15.5% effect size.
2. Primary prespecified analysis: We propose to compare the former placebo arms with the former azithromycin arms, using negative binomial regression. Significance testing is two-sided with an alpha of 0.05, and will be based on permutation testing. (This analysis is identical in every way to the country subgroup analyses conducted in Stage 1). This is restricted to the period from 24 months to 36 months, covering two six-month study intervals.

3. We propose, as a prespecified secondary analysis, a longitudinal comparison of the original placebo communities. We propose to contrast the first four study intervals during which these communities received placebo, to the last two study intervals during which these communities received azithromycin. Analysis will be conducted using negative binomial regression, with a permutation P-value reported (two-sided,  $\alpha=0.05$ ). The community-randomized nature of the trial is thus taken into account.
4. Additional supplementary analyses will be distinguished from the two prespecified analyses above. In particular, the following will be reported:

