  - a. Analysis of the seasonality and timing of deaths: time of death, time of treatment for those who died, and time since treatment for all deaths. We will conduct comparisons of time since treatment conditional on death based on the Cramer-von Mises test (exactly as in Stage 1), additionally comparing across treatment arms and longitudinally. Comparisons of equality of circular means will be used to assess seasonality of death and of treatment, comparing between randomization arms and longitudinally. We will, in particular, focus special attention and reporting to a comparison of phases 1-4 to 5-6 within the placebo arm.
  - b. Analysis will be reported according to the same age classes used in the original study (Keenan et al, NEJM, 2018), i.e. 1-5, 6-11, 12-23, 24-59 months.
  - c. We will examine the difference between phase 5 and 6 in the same way.
  - d. We will report longitudinal analysis of mortality changes in the original azithromycin arm, using a linear predictor of study interval (1—6).
  - e. We will compare estimated treatment effect at a regional level using placebo mortality rates as a predictor.

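### Study A item 4a: a circular mean of treatment dates that pools two rounds about 6 months apart depends on how deaths split between the rounds as well as on when doses were given

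*SAP*

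**What the plan says.** Item 4a of Study A (SAP section 3) lists the dates to be analysed: "time of death, time of treatment for those who died, and time since treatment for all deaths". Its method for season is: "Comparisons of equality of circular means will be used to assess seasonality of death and of treatment, comparing between randomization arms and longitudinally". It then undertakes to "focus special attention and reporting to a comparison of phases 1-4 to 5-6 within the placebo arm". Item 4c adds: "We will examine the difference between phase 5 and 6 in the same way".

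The Protocol sets the dosing rhythm. Section 5.1.1 has treatment "directly observed, oral azithromycin suspension (or oral placebo) every 6 months for 2 years". Section 6.1 allows either a short census campaign or a rolling one, but "each community must be censused every 6 months, so it may not take more than 6 months to complete all communities". The schedule in Protocol 4.3 carries a tolerance of one month either way. For Study A's primary comparison the SAP says: "This is restricted to the period from 24 months to 36 months, covering two six-month study intervals".

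For the circular means, the SAP names no test, sets no minimum resultant length, and specifies neither a comparison by round nor a 6-month circle.

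**The concern.** A circular mean describes season well when dates cluster around one point of the year. Treatment dates cluster around two, about 180 degrees apart. Phases 1-4 hold two rounds of each season and phases 5-6 hold one of each, so both sides of the emphasised contrast pool the two rounds equally. The vectors for the two rounds largely cancel. What remains points towards whichever round preceded more deaths or, when the split is close, in a nearly random direction.

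Two misreadings could follow. A difference in mean treatment date could be reported when the calendar was the same, and a real move of both rounds could be missed. The contrast covers the same periods as the prespecified before-after comparison in the original placebo communities (Study A, item 3), so readers may well look to it for differences in timing.

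**Working it through.** The SAP gives no figure for this analysis, so there is none to reproduce.

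**Inputs.** From SAP section 3: 312 communities per arm, 668 people each, 17% in the age range, 2% mortality per year, 10% annual loss. From Protocol 14.4: 80% treatment coverage as the target. Assumed: about 5% average loss within a year, the spread of dates within a round, and the split of deaths between rounds.

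- Children per arm: 312 × 668 × 0.17 = 35,431.
- Deaths per arm-year: 35,431 × 0.02 = 709.
- Deaths with a dose date, per year: 709 × 0.95 × 0.80 ≈ 538 (phases 5-6). Over two years: about 1,077 (phases 1-4).

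**Geometry.** Let a share p of deaths follow one round and 1 − p the other, with rounds exactly 6 months apart and dates uniform over w months within a round. The resultant length is

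R = |2p − 1| × sin(πw/12)/(πw/12).

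At p = 0.5, R = 0 and the mean date is undefined. With sharp rounds at months 2 and 8, p = 0.51 gives a mean of month 2.0 and p = 0.49 gives month 8.0, both with R = 0.02: a 6-month swing on the same calendar.

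With equal counts and spacing of s months, R = |cos(πs/12)|. At s = 5, R = 0.26 and the mean is month 4.5. At s = 5.9 the mean is month 4.95, and at s = 6.1 it is month 11.05, both with R = 0.03. None of these three means is a date on which sharp rounds would dose anyone.

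**Simulation.** 1,077 against 538 dates, rounds 6 months apart. Spread within a round: a campaign (SD 0.5 month), uniform over 3 months, or rolling over 6 months. Dates were drawn independently, without clustering by community.

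| Split in phases 1-4 / 5-6 | True shift | Result |
|---|---|---|
| 50:50 / 50:50 | none | R about 0.03; means differ by more than 3 months in about half of runs; permutation rejects in 6% (campaign) |
| 50:50 / 50:50 | 1 or 2 months | permutation detects it in 0-9% |
| 52:48 / 48:52 | none | median difference 4.1-5.3 months |
| 55:45 / 45:55 | none | median difference 5.2-5.8 months; permutation rejects in 62-86% |
| 55:45 / 55:45 | 1 or 2 months | campaign: median difference 0.99 and 1.99 months; power 56% and 82% |
| 60:40 / 60:40 | none | median difference 0.1-0.4 month |
| 60:40 / 60:40 | 1 or 2 months | power 95-100% for spreads up to 3 months; 48% and 93% for 6-month rolling |
| 60:40 / 55:45 | none | campaign: permutation rejects in 22%, but the apparent shift is 0.17 month |

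**Alternatives.** For a single round, R = sin(πw/12)/(πw/12) = 0.99, 0.90 and 0.64 for w = 1, 3 and 6 months. Two groups of 709 dates on the same calendar then differ by a median of 0.01-0.08 month. On a 6-month circle (angles doubled), R = sin(πw/6)/(πw/6) = 0.96 and 0.64 for w = 1 and 3, whatever the split, and shifts of 1 and 2 months at 50:50 are detected in 100% of runs for spreads up to 3 months. At w = 6 the doubled resultant is 0, so doubling fails for fully rolling dosing.

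**The case against.** The best defence is that the bad results come from unfavourable splits. If mortality has the same moderate season in both periods, about 60:40, the planned statistic is stable and recovers a real shift. This stands. A reader might infer that the annual mean can never describe treatment timing, or that it always misses a shift. The table contradicts both. The documents give no split. The Protocol's mention of a malaria season (section 5.2.2) hints at some imbalance but does not quantify it.

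Second, item 4a concerns the treatment dates of children who died. If their doses move from mostly one round to mostly the other, that distribution has changed, and a test that says so is not simply a false positive. This also stands. The difficulty is that the statistic cannot separate such a change from a change of calendar.

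Third, the SAP does not state that the purpose is to check whether dosing season explains the before-after result. That use is an inference.

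Fourth, very high false-positive rates can be produced with a Watson-Williams test, but the SAP names no test here and relies on permutation elsewhere. At 50:50 permutation keeps close to its nominal level. Permutation calibrates the P-value; it does not make the mean date more informative.

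Fifth, the SAP does not say that the between-arm comparison is pooled over rounds, and item 4c works on single rounds, where the mean is well defined. (Phases 5 and 6 will differ by about 6 months by design.) The pooling argument is therefore secure only for phases 1-4 against 5-6.

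Finally, the SAP calls these analyses supplementary and keeps them apart from the two prespecified ones, so the consequence is limited.

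**Conclusion.** The concern holds in conditional form. In the emphasised contrast, the circular mean of treatment dates mixes the dosing calendar with the split of deaths between two near-opposite rounds. Near 50:50 it is close to arbitrary. If the dominant round reverses between periods, the means can differ by 5-6 months on an unchanged calendar. With a clear imbalance shared by both periods it behaves acceptably. Which case applies cannot be known from the documents.

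The sizes rest on assumed splits and spreads, independent dates, and spacing of 6 months. Spacing away from 6 months steadies the mean but, with equal counts, places it between rounds or opposite that midpoint. Rolling dosing does not remove the problem, because each community's own two dates remain about opposite.

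Circular means of death dates are not affected by this argument. It would be wrong to infer that any primary or secondary mortality conclusion changes.

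**What to change.** In item 4a, replace the pooled circular mean of treatment dates with season-matched comparisons: phases 1 and 3 against 5, and phases 2 and 4 against 6, with the community as the unit. Between arms, compare phase by phase. Report the split of deaths by round as a separate result, and give the resultant length beside any pooled circular mean that is kept. Doubling the angles is an option only if rounds were short campaigns. The annual circular mean can stay for dates of death.

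The cost is one or two sentences in the SAP and a small change of code, with no new data. The downside is two matched comparisons instead of one pooled figure.

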4.3. Study Schedule

The schedule for examination and treatment is shown below in Table 1:
MORDOR Study Schedule

	MORTALITY		MORBIDITY / RESISTANCE	
	Azithro	Control	Azithro-Plus	Control-Plus
Oral Azithromycin (N/2 communities)	Oral Placebo (N/2 communities)	Oral Azithromycin (N = 15 communities)	Oral Placebo (N = 15 communities)	
MORDOR 0 Jan-15 to Jul-15*	Census Azithro	Census Placebo	Census Swabs Blood Stool Anthropometry Azithro	Census Swabs Blood Stool Anthropometry Placebo
MORDOR 6 Aug-15 to Jan-16	Census Verbal Autopsy Azithro	Census Verbal Autopsy Placebo	Census Azithro NP Swabs, Blood, Stool^a Malaria Collection^b	Census Placebo NP Swabs, Blood, Stool^a Malaria Collection^b
MORDOR 12 Feb-16 to Jul-16	Census Verbal Autopsy Azithro	Census Verbal Autopsy Placebo	Census Swabs Blood Stool Anthropometry Azithro	Census Swabs Blood Stool Anthropometry Placebo
MORDOR 18 Aug-16 to Jan-17	Census Verbal Autopsy Azithro	Census Verbal Autopsy Placebo	Census Azithro NP Swabs, Blood, Stool^a	Census Placebo NP Swabs, Blood, Stool^a
MORDOR 24 Feb-17 to Jul-17	Census Verbal Autopsy Azithro^c	Census Verbal Autopsy Azithro^c	Census Swabs Blood Stool Anthropometry Azithro^c	Census Swabs Blood Stool Anthropometry Azithro^c

Only children aged 1 month to 60 months per community will be treated Arms Azithro+ & Control+: swabs, blood testing, and stool samples or rectal swabs from 40 randomly selected children aged 60 months per community; anthropometry from a cohort of children aged 1 to 60 months per community; NP swabs from 40 individuals aged 7 – 12 years (Niger only)
				

a: Tanzania only b: Niger only c: Decision to treat ALL communities with azithromycin at 24-months if there is a significant mortality difference (in preparation for possible contingent study, Niger only)
				

*: +/- 1 month
				

Chapter 5: Core and Non-Core Study Elements

An overview of core and non-core elements for the mortality and morbidity study is provided here, but will be described in more detail in the following chapters.

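### The linear trend over study intervals 1 to 6 in SAP item 4d has no season term, so a constant difference between half-years would appear as a trend in the continuously treated arm

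*SAP*

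**What the plan says.** SAP section 3, Study A, item 4 lists supplementary analyses, kept apart from the primary analysis (item 2) and the prespecified secondary one (item 3). Item 4d is a "longitudinal analysis of mortality changes in the original azithromycin arm, using a linear predictor of study interval", with intervals numbered 1 to 6. It names no season or calendar covariate, no comparator arm and no significance level. Item 4c reads "We will examine the difference between phase 5 and 6 in the same way" and does not say whether the contrast is within or between arms. Item 4a studies the seasonality of deaths and treatments as a separate analysis.

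On timing, item 2 describes months 24 to 36 as "covering two six-month study intervals". Protocol 6.1 (Census Timing) requires that "each community must be censused every 6 months", and lets a site work over a short discrete period or on a rolling basis, with "all communities completed over a 6-month period, requiring fewer census teams to be active at once". Protocol 4.3, Table 1 gives visit windows about six months wide, for example "MORDOR 6 Aug-15 to Jan-16" and then "MORDOR 12 Feb-16 to Jul-16".

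**The concern.** With censuses six months apart, a given community's intervals 1, 3 and 5 fall in one half of the year and its intervals 2, 4 and 6 in the other. The plan itself treats seasonal mortality as a live question: item 4a tests it, and Protocol 5.2.2 refers to a malaria season. A six-point series that starts in one season and ends in the other has a built-in tilt. If the odd intervals carry the higher mortality, a straight line falls although nothing changed from year to year; if the even intervals do, it rises.

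Item 4d is the planned description of how mortality moved over three years of continued azithromycin. A seasonal tilt there could be taken for a change under treatment. Study B item 4, a longitudinal analysis of always-treated communities, would carry the same risk if modelled in the same way.

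**Working it through.** **1. Reproduce the plan's power, to confirm the inputs.** SAP item 1a gives 312 communities per arm, 668 people with 17% in the age range, 10% yearly loss, 2% yearly mortality, a 20% effect and CV k = 0.51. Child-years per community: y = 668 × 0.17 × 0.9 = 102.2. The standard formula for cluster-randomized rates is

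(c - 1) = (z_a + z_b)² × [(r0 + r1)/y + k²(r0² + r1²)] / (r0 - r1)².

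With r0 = 0.02 and r1 = 0.016, the bracket is 0.000352 + 0.000171 = 0.000523. Dividing by 0.000016 gives 32.7. Then z_b = sqrt(311/32.7) - 1.96 = 1.125, a power of 87.0% against the stated 87%. Item 1b (k = 0.34) gives 81.9% and 81.3% against the stated 80%.

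**2. The false slope.** Let log mortality be flat apart from +a in odd and -a in even intervals, with a = ln(R)/2. Deviations of 1 to 6 from their mean are -2.5, -1.5, -0.5, 0.5, 1.5 and 2.5, with sum of squares 17.5. Their product with (+1, -1, +1, -1, +1, -1) sums to -3. The fitted slope is therefore -3/17.5 × ln(R)/2 = -0.0857 ln R per interval, or -0.429 ln R from interval 1 to 6.

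**3. Precision at the SAP's inputs.** Expected deaths per community-interval: 113.56 children × 1% × 0.975 = 1.107 (5% loss per half-year, half of it on average). Taking CV 0.34 as independent across intervals, SE = sqrt[(1/1.107 + 0.34²)/(312 × 17.5)] = 0.01366.

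**4. False-trend rates.** R is assumed, because the documents give no value. Item 4d states no test, so two-sided 0.05 is used for illustration. The simulated columns use 312 communities, gamma frailty with CV 0.34, 2% mortality a year, community-clustered standard errors and 400 runs.

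| R | Slope per interval | Rate ratio, interval 6 v 1 | z | Discrete census, formula | Discrete, simulated | Six-month roll, simulated |
|---|---|---|---|---|---|---|
| 1.2 | -0.0156 | 0.925 | 1.14 | 21% | 22% | 13% |
| 1.5 | -0.0348 | 0.840 | 2.54 | 72% | 70% | 37% |
| 2 | -0.0594 | 0.743 | 4.35 | 99% | 100% | 79% |

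At R = 1 both simulations reject 5% of the time. Monte Carlo error is at most about 2.5 points (sqrt(0.37 × 0.63/400) = 0.024). A Poisson fit gives rate ratios of 0.925, 0.842 and 0.751 and rejection of 21%, 73% and 99%. With mortality at 1.6% a year (2% less the SAP's 20% effect), the discrete rates are 18%, 63% and 97%. For a sinusoidal season, a six-month roll shrinks the slope to about 63% of its discrete value.

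**5. Other Study A contrasts.** Item 3 compares intervals 1 to 4 (two of each season) with 5 and 6 (one of each), so the seasonal bias on the log scale is 0. The primary analysis compares arms over the same two intervals, so season cancels. For item 4c read within an arm, the apparent ratio with no true change is R itself on a common calendar; R = 2 becomes about 1.53 under a six-month roll.

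**The case against.** The strongest reply is that Table 1 gives windows for visits, not intervals. A community first visited in January 2015 and one first visited in July 2015 have interval 1 in opposite halves of the year, so across communities interval 1 can span the whole calendar. The table also stops at month 24. This stands. A reader might infer from Table 1 that all odd intervals of the trial share one season. The documents support alternation only within a community, or across the trial if Niger used a discrete census. Rolling reduces the artefact but, by the simulation, does not remove it.

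The magnitudes depend on an assumed R, and the artefact is zero if the seasonal peak straddles the census dates so that the half-years balance. That also stands. A reader might take 21%, 72% and 99% as the expected error rates; they are the discrete-census case of a test that item 4d does not specify.

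For mitigation, one can point to item 4a, to the reporting of every visit, and to SAP Statistical considerations, item 2, which allows further models when the negative binomial fit is poor. These make an alternating pattern easier to notice, but none adjusts the slope in 4d, and the last is a general permission that depends on the results. The Stage 1 SAP, to which the primary-outcome analysis defers, is not among the documents, so a season term there cannot be excluded.

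On item 4c, a reader might infer that phase 5 against phase 6 is fully confounded with season. That needs both a within-arm reading, which the text does not state, and a common calendar. A between-arm reading is not confounded.

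**Conclusion.** The point holds for item 4d. As written, its slope absorbs -0.0857 ln R per interval from any constant difference between half-years. At the SAP's own death counts a moderate difference would often look like a trend: about 21%, 72% and 99% for R = 1.2, 1.5 and 2 with a discrete census, and about 13%, 37% and 79% with a six-month roll. This rests on the assumed R, on a season aligned so that the half-years differ, on 2% yearly mortality with CV 0.34, and on the illustrative 0.05 level.

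The reach is limited to supplementary analyses; the mechanism does not touch the Study A primary comparison or item 3. It is also tempting to read 4d as showing whether the benefit of azithromycin grows or wanes. It cannot, with or without a season term: it has no comparator, so it describes mortality in one arm, secular change included. Item 4c is a request for clearer wording, not an error.

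**What to change.** In item 4d, add an odd/even interval indicator or a calendar-season term to the model (presumably negative binomial, as in items 2 and 3). Alternatively compare whole years 1, 2 and 3, each of which holds one interval of each season. With the indicator, the false slope was 0.000 for every R tried on a common calendar; under a rolling census it removes the average seasonal artefact.

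The cost is small. The squared correlation between the linear and alternating terms is 3²/(17.5 × 6) = 0.0857, so the slope variance rises by 1/(1 - 0.0857) = 1.094, about 9%, and the standard error by about 4.6%. No new data are needed.

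State in the SAP that 4d describes a trend in mortality and not in benefit, and record which census mode Niger used. In item 4c, say which contrast is meant and report the former-placebo v former-azithromycin rate ratio by phase. Apply the same season term to Study B item 4 if it is modelled as a trend over intervals.
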